#### **Adverse Event Recording and Reporting**

All adverse events, whether serious or not, will be recorded on source documents and adverse event case report form. The recording period for all serious adverse events starts at the time the subject signs the informed consent. This includes events that emerge during screening. The recording period for a non-serious adverse event starts at the time the subject takes the first dose of study product. The recording period for serious adverse events lasts for 30 days and at least 7 days for non-serious adverse events after the subject's last administration of study product, regardless of relationship to the study product or protocol. The Investigator must follow up as medically necessary on all adverse events, serious adverse events, and other reportable events until the event has subsided or values have returned to baseline, or in the case of permanent impairment, until the condition stabilizes. For serious adverse events, the Investigator will provide all documentation pertaining to the event (*e.g.*, additional laboratory tests, consultation reports, discharge summaries, postmortem reports, etc.) to the Sponsor in a timely manner.

Information about all adverse events, serious and non-serious, including the event's severity, start and stop times/dates, chronicity, relatedness to study product, and any actions taken, must be recorded on the appropriate case report forms. The information recorded will be based on the signs and symptoms detected during the physical

examination and clinical evaluation of the subject as well as information recorded in the subject's diary, when applicable.

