#### Study Schedule:

Events	Screening Baseline	2-weeks*	6-weeks	3-months	18-weeks**	6-Months
Informed Consent,						
Demographics,	X					
Inclusion/Exclusion Criteria, Medical History, Conmeds						
Demographics/Product Use						
Questionnaire	X					
Dentifrice Distribution	X		X	X	X	
Diary Disbursement/Review	X		X	X	X	X
Update of Inclusion/Exclusion						
Criteria, Medical History and			X	X	X	X
Conmeds						
Oral Soft/Hard Tissue Exam	X		X	X		X
Gingival Exam (MGI)	X		X	X		X
Bleeding Exam (GBI)	X		X	X		X
Plaque Exam (PI)	X		X	X		X
Subjective Sensory Evaluation	X		X	X	X	X
Supervised Brushing	X					
Compliance Check		X	X	X	X	X
Product assessment						X
Questionnaire						Λ
Adverse Events			X	X	X	X
Product Weights	X		X	X	X	X

At 2-weeks, subjects will receive a post-baseline compliance call to reinforce product use instructions and study instructions.

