#### 2-week (±3 days) Compliance Phone Contact

Approximately 2 weeks after the baseline visit, study personnel will contact each subject by phone. Study personnel will reinforce the product use instructions and study instructions and will remind the subject of the 6-week visit.

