#### 6-Week Visit (± 7 Days) & 3-Month Visit (± 7 Days)

Subjects will report to the study site with their dentifrice, toothbrush, diary and timer, having refrained from all oral hygiene procedures that morning and from eating, drinking and smoking for approximately 4 hours prior to their appointment time. Their medical history, current medication usage and inclusion/exclusion criteria will be updated and recorded. The dentifrice products will be weighed to assess product use and the diary entries will be reviewed to determine compliance with study requirements. The subject will be questioned about dentifrice use compliance by asking "Your brushing schedule is twice daily (morning and evening), for 1 minute per brushing, using only the toothpaste and toothbrush provided by All Sum Research. Have you deviated from that schedule at all?" (e.g. made any changes or forgotten to use the toothpaste). A "yes" or "no" answer to the question must be obtained. For all "yes" answers, the study site staff must determine what changed. Subjects will be assessed for any AEs they may have experienced since the previous visit.

The subjects will provide a post-baseline sensory evaluation. They will be asked if they have experienced any problems such as burning, stinging, irritation, etc., and, if so, the nature of the effect, severity and onset time (if known) will be recorded. A qualified dental examiner will perform an oral soft and hard tissue examination (OST), followed by gingival, bleeding, and plaque assessments.

The subjects will be provided with one additional tube of toothpaste.

The subjects will be reminded not to use any other oral hygiene products for the duration of the study. Subjects will be scheduled for their next visit and will be instructed to refrain from any oral hygiene procedures the morning of their next visit and to refrain from eating, drinking and smoking for approximately 4 hours prior to their next visit. They will be advised to follow the instructions carefully and return to the study site with their assigned toothpaste, toothbrush, timer and diary for their next appointment. Subjects will be scheduled for their next visit and will receive a reminder call prior to the visit.

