#### 6-Month (± 7 Days)

Subjects will report to the study site with their dentifrice, toothbrush, diary and timer, having refrained from all oral hygiene procedures that morning and refraining from eating, drinking and smoking for approximately 4 hours prior to their appointment time. Their medical history, current medication usage and inclusion/exclusion criteria will be updated and recorded.

Subjects will provide a sensory evaluation as described at the 6-week visit. A qualified dental examiner will perform an oral soft and hard tissue examination (OST), followed by a gingival, bleeding and plaque assessments.

The subject will be questioned about dentifrice use compliance by asking "Your brushing schedule is twice daily (morning and evening), for 1 minute per brushing, using only the toothpaste and toothbrush provided by All Sum Research. Have you deviated from that schedule at all?" (e.g. made any changes or forgotten to use the toothpaste). A "yes" or "no" answer to the question must be obtained. For all "yes" answers, the study site staff must determine what changed. Subjects will be assessed for any AEs they may have experienced since the previous visit.

The dentifrice products will be weighed to assess product use and the diary entries will be reviewed to determine compliance with study requirements. All test products will be collected.

At the 6-month visit, subjects will complete a product questionnaire for informational purposes. This visit completes the subjects' participation in the study.

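### The adverse-event recording period runs 7 or 30 days past last use, but no contact is planned after the 6-month visit, and subjects who leave before week 6 may never be asked

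*Combined protocol and SAP*

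**What the plan says.** **The recording period** (section XII, Adverse Event Recording and Reporting).
- Start, serious events: "The recording period for all serious adverse events starts at the time the subject signs the informed consent".
- Start, non-serious events: "The recording period for a non-serious adverse event starts at the time the subject takes the first dose of study product". First use is the supervised brushing at baseline (section IX).
- End: "The recording period for serious adverse events lasts for 30 days and at least 7 days for non-serious adverse events", counted from the time "after the subject's last administration of study product, regardless of relationship to the study product or protocol".

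**The planned contacts** (section VI, Study Schedule, and section X).
- The schedule row reads "Adverse Events X X X X". The marks fall at 6 weeks, 3 months, 18 weeks and 6 months, with none at baseline or at the 2-week call.
- The 2-week call has this content: "Study personnel will reinforce the product use instructions and study instructions and will remind the subject of the 6-week visit". No adverse-event question is listed.
- At 6 weeks and 3 months: "Subjects will be assessed for any AEs they may have experienced since the previous visit".
- At 6 months the product is collected, and "This visit completes the subjects' participation in the study".

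**The analysis set** (section XIV, Safety Analysis). All randomized subjects form the safety population.

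**The concern.** Safety is part of the primary objective (Study Objectives), and the safety summary is meant to cover everyone randomized. A stated recording period tells the reader of the report which interval the event counts cover. If part of that interval has no planned contact, counts from that part depend on who chooses to call the site, yet the report would present them as coming from the same window.

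This arises in two places. After the 6-month visit the protocol keeps the window open but plans no means of filling it. Before week 6 a subject can be randomized, use the product, leave, and be counted in the safety denominator without having been asked about adverse events. Someone who stops early because of irritation is the subject whose report matters most.

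**Working it through.** The plan gives no figure on this point to reproduce. The check is a day count of the recording period against the planned contacts.

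**Inputs**
- Recording after last use: 30 days (serious) and a minimum of 7 days (non-serious), section XII.
- Visit windows: 2-week call ±3 days; 6-week and 6-month visits ±7 days, section X.
- No oral hygiene on the morning of the 6-month visit, section X.
- About 320 enrolled and 300 expected to complete, section V.
- Assumptions: baseline is day 0; week 6 is day 42; 6 months is day 180 to 183; last use is 1 day before the 6-month visit.

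**End of the window**

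Let d be the day of the 6-month visit and k the days from last use to that visit. Days left after the last planned contact are 30 − k (serious) and 7 − k (non-serious minimum).
- With k = 1: 30 − 1 = 29 and 7 − 1 = 6.
- If the subject did use the product on the visit day (k = 0): 30 and 7.
- If the subject had stopped a week earlier (k = 7): 23 and 0.

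Share of the whole window with k = 1, where d runs from 180 − 7 = 173 to 183 + 7 = 190:
- Serious, 29 / (d − 1 + 30): 29/202 = 14.4% down to 29/219 = 13.2%.
- Non-serious, 6 / (d − 1 + 7): 6/179 = 3.4% down to 6/196 = 3.1%.

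No visit, call or diary is described for these days. The follow-up duty in section XII applies to events already known, and the 24-hour reporting clock for serious events starts when the investigator becomes aware. Neither finds a new event.

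**Start of the window, subjects who attend week 6**
- The first scheduled adverse-event question falls at day 42 ± 7, that is day 35 to 49.
- It asks about the time since the previous visit, which at week 6 is baseline. Days not covered by the question: 0.
- Three further sources cover the same interval: the daily diary, which section XII names as a source for the adverse-event record; the week-6 sensory question, with nature, severity and onset; and the tissue examination, which records change from baseline.
- Consent and first use appear to fall within one attended screening/baseline visit, so the serious-event window before first use is short and under observation.
- What remains is delay: recall of up to 35 to 49 days for anything not in the diary. The diary records oral effects, its comments are voluntary (Product Use Compliance), and its first scheduled review is at week 6.

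**Start of the window, subjects who leave before week 6**
- No safety contact at withdrawal is described. Follow-up of withdrawals caused by an adverse event is left to the investigator's discretion (section XIII).
- The plan allows for about 320 − 300 = 20 losses over six months, or 20/320 = 6.25%. How many would occur before week 6 is not stated, so within that allowance the number lies between 0 and 20.

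**Effect of a question at the 2-week call**

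The call falls at day 14 ± 3, that is day 11 to 17. The recall interval to week 6 becomes 35 − 17 = 18 to 49 − 11 = 38 days, in place of 35 to 49.

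**The case against.** The best case for the plan is that a recording period is not a promise to ask. It obliges the site to record what it learns, and a passive route exists: section IV requires the consent form to name a contact and telephone number, and each subject keeps a copy. Ending participation at 6 months can be read as ending the subject's procedures without ending the investigator's recording duty. The consent pages were removed from the public document and the subject instruction sheet is not shown, so they may tell subjects to report later events. The planned safety analysis is a descriptive summary, and no efficacy result is affected.

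Much of this stands. The two sections are not in flat contradiction, and events after the 6-month visit are not beyond reach. What it does not supply is a planned contact: the days after the visit still rest on spontaneous reports.

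A reader might infer something stronger: that both ends of the window go unobserved, that all subjects spend six weeks outside any adverse-event question, and that an absence of early events would only show that nobody asked. The documents do not support this. The week-6 question covers the interval back to baseline, and the diary, sensory question and tissue examination cover it as well. The wait before the question is a delay in asking; it is not time the question leaves out.

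**Conclusion.** The point holds for the end of the window and, at the start, only for subjects who leave before week 6. For each completer about 29 of 30 serious-event days and 6 of the minimum 7 non-serious days follow the last planned contact, about 13% to 14% and 3% of the respective windows. This assumes last use the evening before the 6-month visit; other stop dates shift it as shown. For attenders the start is covered late, partly by recall. The number leaving before week 6 is unknown.

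This is a minor point: it touches the completeness of safety data and no efficacy conclusion. It is worth acting on because safety belongs to the primary objective and the remedy is cheap.

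**What to change.** 1. Add an adverse-event question to the 2-week call. No new contact is needed. It shortens recall and reaches some subjects who would leave before week 6, though not those who leave before the call or cannot be reached.
2. Reconcile the Study Schedule, the 6-Month visit text in section X and the recording period in section XII, so that the stated period matches the planned contacts. One way is a short telephone contact at the end of the window. If it is timed from last use, as the window itself is, it would also serve subjects who withdraw early. Shortening the stated period would align the text too, but would give up collection after last use.
3. If the sponsor prefers to rely on spontaneous reports after the 6-month visit, say so in section XII, so that the report can describe those days accurately.

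The cost is one brief call per subject, about 320 at most, plus form entry, severity and causality judgement and sponsor reporting for any further event found. The 2-week question adds no contact but carries the same paperwork.

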#### **Serious Adverse Event Reporting**

Any **serious adverse event**, regardless of causal relationship, must be reported immediately to Sponsor no later than 24 hours after the Investigator becomes aware of the serious adverse event) by emailing a pdf of the completed Adverse Event case report form and then confirming by telephone that the email was received. Along with a completed and signed case report form, the Investigator may include the following documentation: pertinent

supporting records such as assessment of the AE/drug relationship, the action(s) taken by the Investigator, case report forms, hospital records, and diagnostic test results.

Follow-up information relating to a serious adverse event must be reported to the Sponsor within 24 hours of receipt by the Investigator by emailing a completed Adverse Event case report form and confirming by telephone that the email was received. The subject will be observed and monitored carefully until the condition resolves, stabilizes, or its cause is identified. The Investigator will also promptly notify the IRB/IEC about the serious adverse event in accordance with IRB/IEC requirements.

#### XIII. SUBJECT COMPLETION AND WITHDRAWAL

#### **Subject Completion**

Only subjects who complete all procedures and comply with all areas of the protocol will be deemed to have completed the study. Subjects will be compensated for their time and travel and for successfully completing all provisions and procedures of the study. If a subject voluntarily withdraws from the study, or if withdrawn by the Investigator for any reason, he/she will be compensated as agreed upon with All Sum Research. Subject compensation will be documented in the Informed Consent and will be approved by the IRB/IEC.

#### **Subject Withdrawal**

Subjects are free to withdraw at any time during the clinical trial. Subjects may also be withdrawn from the study at any time at the discretion of the Investigator and/or the Sponsor. All subject withdrawals will be documented in the study file. Where possible, the reason for the withdrawal will be documented. Any withdrawals as the result of an adverse event will be followed-up at the discretion of the Study Investigator. Withdrawn subjects will not be replaced.

#### **Subject Discontinuation**

A subject will be considered discontinued from the study at any time under the following circumstances:

- Any subject who violates any condition of the entrance criteria after having been entered the study.
- Any subject who develops a confounding concomitant illness (as determined by the subject, Research Coordinator or Investigator) or a serious adverse event.
- Any subject who becomes uncooperative, does not adhere to the requirements of the study protocol, or refuses to complete the study.

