#### **Inclusion Criteria**

Individuals may be included in the study provided they meet all the following inclusion criteria:

- Have provided written informed consent prior to being entered into the study.
- Be between 18 and 70 years of age, male or female.
- Have at least eighteen (18) natural teeth with scorable facial and lingual surfaces as determined by the Examiner. Teeth that are grossly carious, orthodontically banded, exhibiting general cervical abrasion and/or enamel abrasion, or third molars will not be included in the tooth count.
- Have a mean baseline plaque index score ≥ 1.95 as determined by the Soparkar Modification of the Turesky Modification of the Quigley-Hein Plaque Index (PI).
- Have a mean baseline gingival index score of ≥ 1.70 and ≤ 3.0 as determined by the Modified Gingival Index (MGI).
- Presence of  $\geq 10$  bleeding sites upon probing.
- Agree not to have a dental prophylaxis or any other elective, non-emergency dental procedures any time during the study.

- Agree to abstain from the use of chewing gum, mouth rinses, any toothpaste other than the study toothpaste, tooth whitening products (either professional or at home use) and all other oral hygiene other than the study procedures for the duration of the study.
- Agree to refrain from all oral hygiene on the morning of each evaluation visit and to refrain from eating, drinking and smoking for 4 hrs. prior to each evaluation visit.
- Agree to comply with the conditions and schedule of the study.

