#### PRODUCT USE COMPLIANCE

To ensure compliance with product use, each subject will complete a daily diary indicating the time of each tooth brushing for the 6-month duration of the study. The diary will also provide space for voluntary comments about the products and any effects the subject experiences.

The subjects will be requested to return their dentifrice, toothbrush, timer and diary at each exam visit for a compliance check. The dentifrice products will be weighed at initial dispensation and at all subsequent visits to assess product use and subject compliance with study requirements. Based on product weights, subjects who appear to be out of compliance will again be shown how to apply a full ribbon of product to their toothbrush and will be reminded to brush two times daily. To maintain blinding, each subject's dentifrice tube will be inspected to confirm that the overlabel has not been removed. The subjects will also be questioned at each site visit to confirm they have not removed the label and identified the product being used.

Following 2-weeks of product use, subjects will be contacted by phone to remind them of the product use instructions and study instructions.

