#### **Efficacy Analysis**

The primary analysis will be conducted on the population of subjects who complete all study visits. A secondary analysis will be conducted on the intent to treat population; that is, at each time point, all subjects who completed both the baseline evaluation and that evaluation will be included in the analysis. Additional subsets of the subject

population may be analyzed for informational purposes only. Other than the subject inclusion criterion, all analyses will be conducted identically as follows:

For each examination and each index, subjectwise mean Index scores will be obtained by calculating the average of the index scores evaluated at all individual measurement sites within the mouth. In addition to these 'whole-mouth' scores, subjectwise scores will also be obtained by calculating the average index scores over selected subsets of sites within the mouth. These subsets will include: Proximal sites; Marginal sites (MGI and GBI only); Gingival sites (PI only); Facial sites; Lingual sites; Posterior sites; Anterior Facial sites; and Anterior Lingual sites.

All statistical analyses will be based on the subjectwise Index scores. Separate analyses will be performed based on the subjectwise whole-mouth scores, as well as the subjectwise scores obtained from each of the selected subsets of the mouth.

The primary endpoints employed for the treatment comparisons in this study will be the month 6 Index scores. Additional analyses will be conducted on the Index scores collected at other time points. The comparison of the study treatments will employ an analysis of covariance (ANCOVA) model, with the associated baseline Index score included as a covariable. The ANCOVA model will include the factors: subject, treatment, and baseline Index score. Post-ANCOVA pairwise treatment comparisons of the adjusted means will be performed using t-tests utilizing Tukey's adjustment for multiple comparisons. Within-treatment comparisons of the mean baseline Index scores to the mean month 6 (or other post-baseline time point) Index scores will be performed using paired t-tests.

The comparison of the study treatments at baseline for each index will be performed using the same model described above, without the inclusion of the covariable.

All statistical tests of hypotheses will be two-sided, and employ a level of significance of  $\alpha = 0.05$ .

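### Subjects discontinued after randomisation have no planned month-6 exam, so they drop out of both the primary and the intent-to-treat month-6 comparisons

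*Combined protocol and SAP*

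**What the plan says.** All references are to the combined protocol and SAP.

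- **Subject Discontinuation (XIII)** lists the circumstances in which a subject is considered discontinued from the study. They are: "Any subject who violates any condition of the entrance criteria after having been entered the study"; a confounding illness or a serious adverse event; and "Any subject who becomes uncooperative, does not adhere to the requirements of the study protocol, or refuses to complete the study".
- **6-Week and 3-Month Visits (X)**: "Their medical history, current medication usage and inclusion/exclusion criteria will be updated and recorded". The Study Schedule shows the same update at 18 weeks and 6 months.
- **Efficacy Analysis (XIV)**: "The primary analysis will be conducted on the population of subjects who complete all study visits". The secondary set, labelled intent to treat, takes at each time point those with a baseline exam and an exam at that time point. The primary endpoints are the month-6 scores.
- **Product Use Compliance** handles poor compliance differently. Judged by product weight, "subjects who appear to be out of compliance will again be shown how to apply a full ribbon of product to their toothbrush" and are reminded of the brushing schedule. Discontinuation is not mentioned.
- **Protocol Deviations (XV)** covers noncompliance by subjects through reporting and corrective action, again without discontinuation.
- **Inclusion Criteria (V)**: two thresholds are tied to baseline ("Have a mean baseline plaque index score" and "Have a mean baseline gingival index score of"). The third, at least 10 "bleeding sites upon probing", carries no time point.

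**The concern.** Every event on the discontinuation list can happen after randomisation, and some may depend on the assigned product. The protocol asks about burning, stinging and irritation at each site visit. A subject who dislikes a paste may brush less, switch paste or add a rinse. Several entrance criteria are continuing undertakings (no gum, rinse, other toothpaste or elective dental work), so breaches after entry are foreseeable.

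If such subjects leave the study, those left at month 6 are no longer the groups that were randomised. An intent-to-treat analysis would normally show whether that matters. Here the set with that name needs the same month-6 exam, so it cannot serve as a check for these subjects. An exam that was never taken cannot be recovered at analysis.

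**Working it through.** **1. Is a subject removed before month 6 examined at month 6?** The discontinuation list is about leaving the study. What is described after leaving concerns adverse events: Subject Withdrawal leaves follow-up of such withdrawals to the investigator, and Adverse Event Recording and Reporting follows events to resolution. No MGI, GBI or PI exam after discontinuation appears in the Study Schedule or the visit sections.

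**2. Which month-6 set could hold that subject?**

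| Subject | Primary set, month 6 | Set labelled intent to treat, month 6 |
|---|---|---|
| Attends every visit | in | in |
| Misses a middle visit, attends month 6 | out | in |
| Discontinued before month 6 | out | out |
| Event first found at the month-6 visit, exam done | in, if attendance is the test | in |

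The third row is the point. No imputation is described. The last row carries a condition because Subject Completion defines completion by full compliance, while Efficacy Analysis speaks only of attending visits.

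**3. What loss does the plan allow for?** Sample Size gives 320 enrolled for 300 evaluable: (320 − 300)/320 = 6.25%, and 300/(1 − 0.0625) = 320, so the enrolment figure reproduces. With equal allocation an arm has 320/3 = 106.7 subjects. Withdrawn subjects are not replaced.

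**4. How far could such losses move a difference?** If a fraction m of an arm is removed, and those kept differ in mean month-6 score from those removed by d standard deviations, then

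mean(kept) − mean(all) = m × d × SD.

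As a percentage of the mean this is m × d × CV. The CVs in Sample Size are 7.2% (MGI), 18.1% (PI) and 61.3% (GBI). The documents do not give d or the split of losses between arms. Both are assumptions here, as is counting all 20 planned losses as discontinuations under this rule.

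| Assumed pattern of 20 losses | d | MGI | PI | GBI |
|---|---|---|---|---|
| 6.25% per arm, same kind of subject | any | 0 | 0 | 0 |
| 6.25% per arm, opposite direction in the two arms compared (2 × 0.0625 = 0.125) | 0.5 | 0.5% | 1.1% | 3.8% |
| as above | 1 | 0.9% | 2.3% | 7.7% |
| All in one arm (20/106.7 = 0.1875) | 0.5 | 0.7% | 1.7% | 5.7% |
| as above | 1 | 1.4% | 3.4% | 11.5% |

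For example, 0.1875 × 1 × 61.3% = 11.5%. These shifts can be set beside the 20% difference used for planning. They may go either way. Removing subjects who stopped because of irritation may flatter an arm; removing subjects who added a rinse may penalise it. Adjustment for baseline takes out only the part that baseline explains. Larger losses scale the figures up.

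**The case against.** **Non-adherence does not plainly end participation.** Product Use Compliance re-instructs, the visit sections only require staff to find out what changed, and Protocol Deviations calls for reporting and corrective action. A site may well keep most non-adherent subjects. This stands. It narrows the point on non-adherence to a conflict between sections, which as written leaves removal to site judgement. It does not touch serious adverse events or confounding illness.

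**The secondary set is not as exposed as the primary one.** This is also right in part. The secondary set keeps a discontinued subject at visits already attended, and at month 6 it keeps those who missed only a middle visit. The two sets are equally exposed only for subjects removed before month 6, but month 6 is where the primary endpoints lie.

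**A stronger reading is tempting.** The bleeding criterion has no time point, and the criteria are updated at each site visit. A reader might infer that a subject who improves to fewer than 10 bleeding sites must be removed, so that responders leave, more of them from the better arm. The documents do not support this:

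- The inclusion criteria govern who may enter.
- Nothing says that a later count below 10 is a violation.
- The update is listed with medical history and medication, not described as re-scoring.
- The 18-week visit updates the criteria but has no bleeding exam.
- Reducing bleeding is part of the primary objective, so the inference would make success a violation.

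What remains is a missing qualifier.

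**Conclusion.** The point holds in this form: subjects discontinued before month 6 have no month-6 exam planned and are absent from both month-6 comparisons. The events that remove them come after randomisation and may be related to treatment. The direction of any bias is unknown.

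Its size is also unknown. At the plan's own loss allowance, and under the assumptions shown, it runs from nothing to 1.4% of the mean for MGI, 3.4% for PI and 11.5% for GBI. The top of each range needs every loss in one arm and a full standard deviation between those kept and those removed. Bleeding is the most exposed index because it is the most variable. This is an inexpensive improvement to make before conduct, not a flaw that by itself invalidates the trial.

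**What to change.** 1. In Subject Discontinuation, separate stopping product use from leaving the study. Whatever stopping rule the sponsor keeps, state that these subjects, unless they withdraw consent, are still invited to those of the 6-week, 3-month and 6-month exams that remain.
2. In Efficacy Analysis, state that subjects examined at month 6 after discontinuation are included, as randomised, in the month-6 intent-to-treat analysis. The existing definition of that set can admit them once the exam exists, so no new set is needed.
3. Reconcile Subject Discontinuation with Product Use Compliance and Protocol Deviations, so that sites handle non-adherence in one way. Which rule is kept is for the sponsor.
4. As a minor clarification, state that the bleeding-site threshold, like those for PI and MGI, applies at baseline only.

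The cost is protocol wording and a few exams. If all 20 planned losses were of this kind, left before week 6 and accepted, that is at most 20 × 3 = 60 exams. Some scores will come from subjects no longer on product and may dilute the intent-to-treat difference. Subjects who decline the exam remain missing.
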